8.2 SETTING

8.2.1 Study sites

The PASS is intended to be available to paediatric hospitals and paediatric departments of European Economic Area member states, where VTE paediatric patients under 2 years of age are treated, depending on country regulations and requirements. Approximately 30 paediatric study sites with experience in VTE anticoagulation treatment and prevention will be selected and initiated by Q4 2022. Every effort will be made to identify sites where paediatric use of DE is available.

The selection of study sites for the 1160.307 study will be focused on specialised paediatric units treating neonates, infants, and young children.

1160.307 PASS NIS Protocol

Proprietary confidential information © 2024 Boehringer Ingelheim International GmbH or one or more of its affiliated companies

Previous experience from the DIVERSITY and prevention of secondary VTE studies support the assumption that approximately 30 specialised paediatric sites focusing on treatment of neonates and infants with VTE risk factors will be able to enrol and collect safety data from overall 50 evaluable children administered DE for VTE treatment and prevention. In addition, experience from the previous dabigatran VTE paediatric program indicates on a potential varying enrolment rate in the selected sites and variations in the clinical management mainly in terms of duration of anticoagulation based on investigator's judgment. However, these variations related to the baseline clinical conditions underline acute VTE event or VTE risk factors that affect safety outcomes, e.g., bleeding events rate in patients with thrombophilia is usually lower than in unselected VTE population under anticoagulation [R21-0986]. The collected safety data from a variety of paediatric units with early age children will reflect routine medical care in EU/EEA when receiving DE anticoagulation.

Based on the previous BI VTE program experience, neonates and infants with acute VTE requiring DE administration are localised in the following paediatric units:

- neonatology departments, where target conditions are umbilical thrombosis, cerebral vein thrombosis, central line related-VTE, etc.
- paediatric surgery, paediatric cardiology, paediatric cardio- surgery, intensive care units, and paediatric haematology departments where target conditions are central line / implantable devices related-VTE, cyanotic congenital heart disease, venous malformations, leukaemias etc.

Patients who require anticoagulation for secondary VTE prevention are evaluated mostly in paediatric haematology, paediatric cardiology, and paediatric cardio-surgery departments.

During the approximate 1.5-year enrolment period every effort will be made to support investigators to include the paediatric patients requiring dabigatran anticoagulation in this study. These efforts will include communications with investigators using digital resources and face to face communications, presentation of the results and enrolment strategies of the previous published studies on DE, focused on early age children [P20-07911].

8.2.2 Study population

Paediatric patients from birth to < 2 years of age considered by investigator after screening as eligible for DE treatment of acute VTE or secondary prevention of recurrent VTE will be enrolled in the PASS and evaluated for up to 3 months in case of acute VTE treatment, and up to 6 months in case of prevention of recurrent VTE.

Patients after completion of acute VTE treatment may continue anticoagulation as secondary VTE prevention due to unresolved VTE risk factors in accordance with investigator's judgment. Total observational period for this group, which include VTE treatment and prevention will be also up to 6 months duration. Further anticoagulation, if required due to unresolved VTE risk factors, will be continued outside the study setting.

Inclusion criteria:

- Written informed consent from parents/care givers,
- Children from birth to less than 2 years of age,
- Initiation of DE administration:
 - for treatment of VTE or/and
 - prevention of recurrent VTE due to presence of unresolved clinical VTE risk factor(s).

Exclusion criteria:

1160.307 PASS NIS Protocol

- Participation in any Randomised Clinical Trial or use of any investigational product,
- Any contraindications to DE according to the EU SmPC.

Paediatric population will be stratified into two groups according to the EU DE SmPC:

- children anticoagulated with dabigatran due to acute VTE treatment
- children anticoagulated with dabigatran for prevention of recurrent VTE due to the presence of an unresolved VTE clinical risk factor.

Patients who completed acute VTE treatment and continued DE anticoagulation due to unresolved VTE risk factors will be considered as one unique patient. However, safety outcomes of each anticoagulation period will be evaluated within the corresponding cohort.

The target sample size for the study is considered to be 50 evaluable patients enrolled from approx. 30 paediatric sites over an approximate 1.5-year period with a total approximate 2-year study duration.

The enrolment period is planned from Q4 2022 (FPI) to the Q2 2024 (LPI) depending on the availability of DE paediatric formulation (granules) on the market.

8.2.3 Study visits

The study is designed as a non-interventional study based on newly collected data and no study related visits are planned. New data collection will reflect routine medical care standards in the EU/EEA paediatric units.

The safety data will be collected during the study observational period defined in the Section 8.1 "Study design". Patients will not be followed outside the observational period.

In order to assure assessment of representativeness of the PASS, all patients under 2 years who required anticoagulation and sign informed consent will be screened for potential participation in the study. During the screening part of the Screening/Baseline visit, screening details will be entered in the Screening Log, which will contain demography, baseline conditions which required anticoagulation and final conclusion on study eligibility with comments on screening failure if not enrolled in the PASS. If a patient completes all study entry criteria, the investigator will proceed with conduction of a baseline part of the Screening/Baseline visit and the patient will enter an observational study period.

Registration of the safety data will be performed at the following visits of both VTE treatment and secondary VTE prevention cohorts:

- Baseline part of Screening / Baseline visit: index date (initiation of DE administration).
- Follow up visits:
 - At approx. 6 weeks or 3 months after initiation of DE administration for acute VTE treatment based on investigator judgment.
 - At approx. 3 or 6 months of DE administration for prevention of recurrent VTE based on investigator judgment.

Patients who continued secondary VTE prevention after acute VTE treatment will conduct two follow up visits: at the end of DE treatment for acute VTE, at discontinuation of DE for secondary VTE prevention or after 6 months of DE administration, whichever occurs first.

Safety data for these patients will be registered for this cohort at the following visits:

- Baseline part of the Screening / Baseline visit: index date (initiation of DE administration).
- Follow up visit(s).

1160.307 PASS NIS Protocol

Duration of the observational period for this group. will be performed until DE administration discontinuation + 3 days of REP or planned end of 6-month observation time, whatever occurs earlier. Patient who completed acute VTE treatment and continued DE anticoagulation due to unresolved VTE risk factors will be considered as one unique patient. However, safety outcomes of each anticoagulation period will be evaluated within the corresponding cohort.

Final Study Visit is defined as a follow up visit conducted after the end of the observational period.

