8.7.1 Main analysis

As this is a descriptive non-interventional, single-arm study, no hypotheses will be tested, rather all variables will be presented in summary using descriptive statistics (absolute and relative frequencies, means, standard deviations, medians, ranges, minimum and maximum values, 95% confidence intervals [CI] and incidences as appropriate for the nature of the variables (i.e., categorical, or continuous))

Safety outcomes will be summarized as incidence with 95% CIs (using Wilson method). All AE/ verbatim terms will be recorded and coded using the Medical Dictionary for Regulatory Activities (MedDRA). Analysis of AEs and other outcomes will be based on treatment emergent events and on all patients, who were treated with dabigatran at least once. Treatment-emergent events are defined as events occurring from start of DE administration (index date) up to DE administration discontinuation + 3 days of Residual Effect Period (REP) or switch to other anticoagulation therapy or planned end of observation time, whatever occurs earlier.

Concomitant medications will be coded according to the World Health Organisation Drug Dictionary (WHO-DD).

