- Disappearance of the event even though the study drug treatment continues or remains unchanged.

Intensity of adverse event

The intensity of the AE should be judged based on the following:			
Mild:	Awareness of sign(s) or symptom(s) which is/are easily tolerated		
Moderate:	Enough discomfort to cause interference with usual activity		
Severe:	Incapacitating or causing inability to work or to perform usual activities		

1160.307 PASS NIS Protocol

Proprietary confidential information © 2024 Boehringer Ingelheim International GmbH or one or more of its affiliated companies

Pregnancy:

Not applicable.

Collection of AEs

The study design is of a non-interventional nature and the study is conducted within the conditions of the approved marketing authorization. Sufficient data from controlled interventional trials are available to support the evidence on the safety and efficacy of the studied BI drug. For this reason, the following AE collection and reporting requirements have been defined.

The following must be collected by the investigator in the eCRF from signing the informed consent onwards until the end of the study:

- all AEs and SAEs,

All AEs including those persisting after study completion must be followed up until they are resolved, have been sufficiently characterized, or no further information can be obtained.

Expedited Reporting of AEs to Pharmacovigilance

The following must be reported by the investigator on the NIS AE form from signing the informed consent onward until the end of study and provided to BI unique entry point:

Type of Report	Timeline
All SAEs in patients exposed to dabigatran etexilate	immediately within 24 hours
All non-serious AEs in patients exposed to dabigatran etexilate	7 calendar days

The same timelines apply if follow-up information becomes available for the respective events. In specific occasions the Investigator could inform the Sponsor upfront via telephone. This does not replace the requirement to complete the NIS AE form.

Information required

For each reportable adverse event, the investigator should provide the information requested on the appropriate eCRF page and the NIS AE form.

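### The protocol's rules conflict on when a child's safety record closes, so bleeds late in the outcome window may go uncollected at some sites

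*Protocol*

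**What the plan says.** **The outcome window.** Section 8.1 starts it at the first DE administration. It ends three days after DE is discontinued or switched (the residual effect period, REP) or at the planned end of observation, whichever comes first. Sections 8.3.1 and 8.3.2.3 repeat this. For children who go on from acute treatment to prevention, Section 8.2.3 runs the period "until DE administration discontinuation + 3 days of REP or planned end of 6-month observation time, whatever occurs earlier".

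**When safety data are registered (Section 8.2.3, repeated in the Abstract).**
- Acute treatment: "At approx. 6 weeks or 3 months after initiation of DE administration for acute VTE treatment based on investigator judgment".
- Prevention: "At approx. 3 or 6 months of DE administration for prevention of recurrent VTE based on investigator judgment".
- Treatment followed by prevention: two follow-ups, one at the end of acute treatment and one "at discontinuation of DE for secondary VTE prevention or after 6 months of DE administration, whichever occurs first".

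**What happens after the window.** Section 8.2.3 says "Patients will not be followed outside the observational period", as do Section 8.1 and the Abstract. It closes with "Final Study Visit is defined as a follow up visit conducted after the end of the observational period".

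**Adverse event collection.** Section 10.2 says of all AEs and SAEs: "The following must be collected by the investigator in the eCRF from signing the informed consent onwards until the end of the study".

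**The concern.** The primary outcome is the incidence of any bleeding in the window, and the secondary outcomes are the incidences of AEs and SAEs. The window has a defined last day for each child, but no listed follow-up is placed on or after that day when DE stops early. The one visit that is placed there, the Final Study Visit, is not identified with any listed follow-up. It also sits beside a sentence that rules out following children past the window.

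About 30 sites are planned, and two of them could close the record at different points while each complies with some sentence of the protocol. Any resulting loss runs one way, because an event that is not collected can only lower the reported incidence. In a study whose purpose is to describe safety, that is the unfavourable direction.

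**Working it through.** The protocol states no figure on this point, and the sample size rests on anticipated usage, so there is no planned calculation to reproduce. The check compares the rules and then sizes the gap.

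**1. Can the rules all be met?** Take a child on treatment followed by prevention who stops DE on day D, before 6 months.
- Visit list: the second and last follow-up is on day D.
- Window: ends on day D + 3.
- Final Study Visit: a follow-up held after day D + 3.
- No-follow-up sentence: nothing after day D + 3.

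If the Final Study Visit is the second listed follow-up, its timing conflicts with the visit list. If it is a third contact, it conflicts with the count of two follow-ups. Either way it conflicts with a literal reading of the no-follow-up sentence.

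**2. How much of the window follows the visit?** Let V be the day of the last scheduled capture, D the day DE stops, and C the planned end of observation.

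- Window length W = min(D + 3, C)
- Days after the visit = W − V; share = (W − V) / W

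Visit on the day DE stops, 6-week course: V = D = 42, W = 45, so 3 / 45 = 6.7%.

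DE continued to the 6-month limit (30-day months assumed): V = D = C = 180, W = 180, so 0 / 180 = 0%.

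If the only visit comes before DE stops, the days after it are D − V + 3 (when the limit C does not bind). The protocol does not say how often that would occur, so no typical size can be given.

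**3. What does one missed child do to the estimate?** With 50 evaluable children, one child is 1 / 50 = 2 percentage points. The counts below are illustrative; the intervals are 95% Wilson, the method named in Section 8.7.1.

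| Children with a bleed | Incidence | 95% interval |
|---|---|---|
| 0 of 50 | 0% | 0.0 to 7.1% |
| 1 of 50 | 2% | 0.4 to 10.5% |
| 5 of 50 | 10% | 4.3 to 21.4% |
| 6 of 50 | 12% | 5.6 to 23.8% |

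The 2 points apply only to a child whose sole bleed is the missed one. A child with another recorded bleed already counts.

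**4. A related mismatch.** Section 8.7.1 ends the treatment-emergent period at "3 days of Residual Effect Period (REP) or switch to other anticoagulation therapy or planned end of observation time", with no three days after a switch, whereas Sections 8.1, 8.3.1 and 8.3.2.3 include them. The day on which a switching child's window closes is therefore also not fixed. A capture made after switch + 3 days would cover both definitions.

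**The case against.** The strongest reply is that the protocol already provides a contact after the window. The Final Study Visit is defined that way in Section 8.2.3 and the Abstract, and no sentence says the record closes at the discontinuation visit. This stands in part. A site that follows the definition would pick up a late bleed. It does not settle the matter, because the visit list and the no-follow-up sentence point the other way and Section 8.2.3 also says that no study-related visits are planned.

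Second, capture does not depend only on visits. Bleeds come from patient files, and Section 10.2 requires SAEs to be reported within 24 hours and non-serious AEs within 7 days. This stands for any event the site learns of. It helps less with minor bleeding at home, which the primary outcome also counts. Section 8.3.2.3 asks parents to report missed doses, and the protocol text shown has no matching instruction for bleeds.

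Third, a reader might take Section 10.2 as a further contradiction. It is not one. Collecting AEs to the end of the study, and following known AEs to resolution, is compatible with analysing only events that began in the window.

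Fourth, a reader might build a large uncovered share by assuming one 6-week visit and a much later stop. The documents do not support that as a measure of size. The Abstract allows more than one follow-up visit, the 6-week and 3-month times mirror the treatment durations in Section 8.1, and the investigator chooses between them. Nor does a full 3-month acute course clearly leave residual days, since Section 8.1 limits acute observation to 3 months.

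**Conclusion.** The conflict is real. For a child on treatment followed by prevention who stops DE before 6 months, the listed timing, the no-follow-up sentence and the Final Study Visit definition cannot all be met as written. One compliant reading leaves the residual days with no scheduled capture of the primary outcome. The same reading leaves later time on DE uncaptured if a site's only visit precedes DE stop.

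The size is modest and conditional: 3 of 45 days (6.7%) for a 6-week course ending at the visit, none for a child on DE to the 6-month limit, and 2 percentage points for each child whose only bleed is lost at n = 50. How many children would be affected cannot be derived from the protocol. Site instructions in the eCRF completion guidelines or the data management plan might narrow the gap, but they are not available here.

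A reader might infer that bleeding will be under-counted. The documents support only that it can be, at sites that take the narrower reading and do not otherwise learn of the event. A reader might also infer that unobserved time inflates a person-time denominator. Section 8.7.1 plans incidences with Wilson intervals, which are for proportions, and states no person-time denominator. The effect would be on the count of children with events.

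**What to change.** Reconcile the Abstract and Sections 8.1 and 8.2.3 so that one event closes each child's record:

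- State that every child has one closing data capture, called the Final Study Visit. It is done by record review or telephone after that child's observational period has ended (discontinuation or switch + 3 days, or the planned end of observation). It covers all bleeding events and AEs with onset in the window.
- Replace the sentence ruling out follow-up beyond the observational period with one saying that events with onset after that period are not included in the analysis.
- Give the end of the window after a switch the same wording in Section 8.7.1 as in Section 8.1.

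Treatment, care and clinic visits are unaffected. The cost is wording in the protocol and the eCRF guidelines, plus one short record check or call for a child with no routine contact after the window, at most about 50 in all. With the capture in place, the part of the window without scheduled collection is zero days for every child.

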8.2.4 Study discontinuation

Boehringer Ingelheim reserves the right to discontinue the study overall or at a particular study site at any time for the following reasons:

- 1. Failure to meet expected enrolment goals overall or at a particular study site
- 2. Emergence of any effectiveness/safety information that could significantly affect continuation of the study, or any other administrative reasons
- 3. Violation of Good Pharmacoepidemiology Practice (GPP), the study protocol, or the contract by a study site, investigator, or research collaborator, disturbing the appropriate conduct of the study

The investigator/the study site/research collaborator will be reimbursed for reasonable expenses incurred in case of study/site termination (except in case of the third reason).

8.3 VARIABLES

8.3.1 Exposures

As per inclusion criteria, all patients in this single arm study will receive DE and will be evaluated as such unless there is no documentation of DE administration as per CRF.

Dabigatran exposure is defined as from start of DE administration (index date) up to the DE administration discontinuation + 3 days of REP or switch to other anticoagulation therapy + 3 days of REP or planned end of observation time whichever occurs earlier.

Dabigatran exposure for the VTE treatment group planned up to a 3-month period and for the prevention of recurrent VTE group up to 6 months (see Section 8.1 "Study design").

8.3.2 Outcomes

All outcome events collected in this PASS are considered as safety outcomes.

1160.307 PASS NIS Protocol c3592 Proprietary confidential information © 2024 Boehringer Ingelheim International GmbH or one or more of its affiliated companies

8.3.2.1 Primary outcomes

• The incidence of any bleeding events defined as Major Bleeding Events (MBE) or Non-Major Bleeding Events (Non-MBE).

Bleeding assessment

In accordance with routine medical care patients on anticoagulation will be carefully assessed for signs and symptoms of bleeding.

In context of this clinical practice study with no blinded adjudication of outcome events it is planned to record bleeding events, as documented in the patient files. Thus, it is planned to differentiate bleeding events as a Major Bleeding Event (MBE) and a Non-Major Bleeding Event (Non-MBE) using the clearly defined criteria for MBEs and Non-MBEs by the Perinatal and Paediatric Haemostasis Subcommittee of the SSC of the ISTH.

Major bleeding defined as,

- Fatal Bleeding,
- Clinically overt bleeding associated with a decrease in haemoglobin of at least 2 g/dL (20 g/L) in a 24-hour period,
- Bleeding that is retroperitoneal, pulmonary, intracranial, or otherwise involves the central nervous system,
- Bleeding that requires surgical intervention in an operating suite.

Non- Major bleeding defined as,

- Any overt or macroscopic evidence of bleeding that does not fulfil the criteria for major bleeding.

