Patients after completion of acute VTE treatment may continue anticoagulation due to unresolved VTE risk factors. The duration of the VTE treatment and secondary VTE prevention periods will be based on investigator judgement. Total duration of the observational period for this group will be performed until DE administration discontinuation + 3 days of REP or planned end of 6-month observation time, whatever occurs earlier.

Patient who completed acute VTE treatment and continued DE anticoagulation due to unresolved VTE risk factors will be considered as one unique patient. However, safety outcomes of each anticoagulation period will be evaluated within the corresponding cohort.

Anticoagulation of more than 6-month duration, if required due to the presence of unresolved VTE risk factors, will not be covered in this study setting.

The duration of anticoagulation outlined in this PASS study is in accordance with international guidelines for management of VTE paediatric patients [P19-00949], results and experience of the previous DE registrational studies, and reflect routine VTE paediatric care. The recommended duration of anticoagulation treatment is up to 3 months for children above one year of age. For neonates and infants (children under 1 year), the usual recommended treatment duration is 6 weeks. However, it may be extended, if the VTE clinical risk factors are unresolved at the end of the 6-week treatment period. Recommendations on the duration of anticoagulation for prevention of VTE recurrence depend on the presence of unresolved VTE clinical risk factors and may continue for an indefinite period of time. Final decision on the duration of VTE treatment and /or secondary prevention periods will be based on investigator's judgment.

Safety data collection will be conducted at Screening/Baseline and Follow up visits for both VTE treatment and prevention of recurrent VTE groups. Visit details provided in the Section 8.2.3. "Study visits".

The study is observational and does not entail any change in prescribing pattern or management policies which are left to the discretion of the treating physician. No special evaluation procedure is required.

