8.3.2.3 Further outcome

• To assess acceptability and tolerability of paediatric formulation.

Acceptability is defined as the overall ability and willingness of the patient and/or parent (legal guardian) to use the medicinal product as intended.

Tolerability is measured as premature treatment discontinuation, treatment interruption, and adherence to trial medication.

Assessment of acceptability and tolerability.

The overall clinical assessment of acceptability and tolerability will be performed by the parent / legal guardian and investigators by completing a standardized questionnaire. In between baseline and study final visits, the parent /legal guardian will be asked to document any failed or missed intake of medication (e.g., the patient did not swallow the medication, or doses missed, etc.) and provide this documentation to the investigator. The parent / legal guardian will be instructed to inform the

1160.307 PASS NIS Protocol

Proprietary confidential information © 2024 Boehringer Ingelheim International GmbH or one or more of its affiliated companies

investigator immediately if two or more consecutive doses of study medication are missed or not taken correctly.

Assessment of the representativeness of the study cohort.

Screening Log with details of all patients requiring anticoagulation due to acute VTE treatment and/or secondary VTE prevention will be used for assessment of the representativeness of the study cohort, when all required anticoagulation patients will be compared with patients enrolled in the PASS.

All parents/legal guardians will be asked to sign informed consent before the screening procedures. Screening Log will contain demography, details of conditions that require anticoagulation, conclusion on entry in the PASS or comments on reasons for screening failure.

The safety outcomes will be evaluated based on the on-treatment period, i.e., from start of DE administration (index date) up to DE administration discontinuation + 3 days of REP or switch to other anticoagulation therapy + 3 days of REP or planned end of observation time, whatever occurs earlier.

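### Minor bleeds at home reach the primary outcome only if a parent happens to mention them, so the any-bleeding incidence may be understated by an unknown amount

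*Protocol*

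**What the plan says.** Protocol section 8.3.2.1 makes the incidence of any bleeding, MBE or Non-MBE, the primary outcome. Non-MBE is "Any overt or macroscopic evidence of bleeding that does not fulfil the criteria for major bleeding". The definition does not require that care was sought, so a minor bleed at home qualifies.

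On ascertainment, the same section says "In accordance with routine medical care patients on anticoagulation will be carefully assessed for signs and symptoms of bleeding" and, noting that there is no blinded adjudication, that "it is planned to record bleeding events, as documented in the patient files".

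Section 8.3.2.3 sets up a parent record for the further outcome of acceptability and tolerability: between the baseline and final visits, "the parent /legal guardian will be asked to document any failed or missed intake of medication". Parents are also to inform the "investigator immediately if two or more consecutive doses of study medication are missed or not taken correctly". Neither instruction mentions bleeding.

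Section 8.2.3 places follow-up for the acute cohort "At approx. 6 weeks or 3 months after initiation of DE administration for acute VTE treatment based on investigator judgment" and for the prevention cohort "At approx. 3 or 6 months of DE administration for prevention of recurrent VTE based on investigator judgment". Section 8.1 adds: "No special evaluation procedure is required".

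Four other provisions bear on the point:
- The Abstract (Variables, follow-up list) includes bleeding events with their location.
- Section 8.4 allows newly collected data as well as data from medical records.
- Section 10.2 requires the investigator to enter all AEs in the EDC system and to keep records of them in the patient files.
- Section 8.10.2.1 requires all eCRF data to come from source documents.

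**The concern.** The outcome covers every visible bleed, but the described route to it covers only bleeds that reach the patient file. A nosebleed or gum bleed at home gets there only if a parent raises it, perhaps months later. The protocol gives parents a written record and a call-in rule for missed doses, which serve a further outcome. It provides nothing comparable for the primary one.

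An unreported bleed can only lower the any-bleeding incidence, so the error makes DE look safer, and the Wilson interval does not reflect it. Section 8.7 says that results will be read alongside DIVERSITY and the secondary prevention study. If bleeds were captured differently there, that reading would be distorted; the protocol does not say how those studies captured them. Because this is a matter of data collection, no later analysis can recover a bleed that was never recorded.

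**Working it through.** **Step 1: what each provision does for a minor home bleed.**

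| Provision | Counts a bleed the parent mentions? | Prompts the parent to mention it? |
|---|---|---|
| Bleeds taken from patient files (8.3.2.1) | Yes, once entered | No |
| Routine-care assessment (8.3.2.1) | Yes | Only when the child is seen; no parent question is stated |
| Bleeding item at follow-up (Abstract) | Yes | Not stated |
| All-AE duty (10.2) | Yes | No; it governs events the investigator knows of |
| Parent record and call-in rule (8.3.2.3) | Not applicable | For doses only |

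Capture of home bleeds is therefore passive. It is not excluded.

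**Step 2: the plan's own figure.** The 50 evaluable patients in section 8.5 rest on anticipated usage and feasibility. No bleeding rate, precision or power is stated, so there is nothing to reproduce. Section 8.7.1 gives the estimator: incidence with a 95% Wilson interval.

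**Step 3: illustration of size.** Let p be the true any-bleeding incidence, m the share of bleeding patients with a clinically seen bleed (all captured), and s the share of home-only bleeders who are captured. Then

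reported incidence = p × (m + (1 − m) × s).

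The documents give none of p, m or s; all three are assumptions. Coverage is the exact binomial probability, at n = 50, that the nominal 95% Wilson interval contains p.

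| p | m | s | Calculation | Reported | Bias (points) | Coverage |
|---|---|---|---|---|---|---|
| 10% | 0.50 | 0.50 | 0.10 × 0.75 | 7.5% | −2.5 | 98% |
| 20% | 0.50 | 0.75 | 0.20 × 0.875 | 17.5% | −2.5 | 94% |
| 20% | 0.50 | 0.50 | 0.20 × 0.75 | 15.0% | −5.0 | 89% |
| 20% | 0.50 | 0 | 0.20 × 0.50 | 10.0% | −10.0 | 57% |
| 30% | 0.25 | 0.75 | 0.30 × 0.8125 | 24.4% | −5.6 | 89% |
| 30% | 0.25 | 0.50 | 0.30 × 0.625 | 18.8% | −11.2 | 61% |
| 30% | 0.25 | 0 | 0.30 × 0.25 | 7.5% | −22.5 | 1% |

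With s = 1 the bias is zero. For scale, the Wilson intervals with full capture are 11.2–33.0% for 10/50 and 19.1–43.8% for 15/50. A shortfall of 2.5 points is small against those widths; one of 10 points or more is not.

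**Step 4: how far the interval would mislead.** If the true incidence were 30%, observed counts of 8, 9, 11 and 13 out of 50 would give Wilson intervals of 8.3–28.5%, 9.8–30.8%, 12.8–35.2% and 15.9–39.6%. Of these, only 8/50 excludes 30%.

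**The case against.** The strongest reply is that the protocol does more than abstract charts. Bleeding is a listed follow-up item, routine care includes bleeding assessment, new data may be collected, and all AEs go into the files and the EDC system. The phrase about patient files follows the remark on blinded adjudication, so it can be read as taking bleeds as recorded, without central review, and not as shutting out parent reports. The follow-up times are data collection points; routine contacts in between also generate records, and section 10.2 sets a 7-day timeline for non-serious AEs. The eCRF guidelines and the data management plan are not shown and may word a bleeding question. Many acute patients are treated in neonatology, surgery or intensive care, so the share of bleeds at home is unknown. The illustration also treats capture as one event per child; a child with several bleeds needs only one to be recorded.

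Much of this stands. A reader might infer that home bleeds are lost, or that the primary incidence is certainly biased downward. The documents do not support either: a bleed that a parent mentions should become a file entry and count, and if most are mentioned the effect is small.

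What remains is that these provisions act on bleeds already known to the site, and none that is stated elicits one from the parent. Section 8.9 concedes incomplete medical records in general, but its measures (completion guidelines and follow-up of missing data) cannot be relied on to reveal a bleed nobody reported, and it names neither bleeding nor the direction of error. The non-interventional design is no bar, since a parent record and a standardised questionnaire are already in the protocol.

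**Conclusion.** The point holds in a limited form. As described, ascertainment of minor home bleeds is passive, and any loss lowers the any-bleeding incidence, so the primary result may be understated by an unknown amount. The effect falls mainly on Non-MBE; major bleeds would normally come to medical attention.

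In the scenarios tabulated, the shortfall runs from 2.5 points (coverage still 94–98%) to 22.5 points at the extreme of no home capture. These figures show sensitivity to assumed inputs and do not estimate the actual bias. This is a cheap improvement worth making, not a defect that invalidates the study.

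**What to change.** 1. In section 8.3.2.3, add a bleeding line (date, site, whether care was sought) to the existing parent record, and have the investigator review it at each follow-up.
2. In section 8.3.2.1, state that parent-reported bleeds count once entered in the patient file.
3. Flag in the eCRF how each bleed was first identified, by parent record or clinical contact. Show the primary incidence overall and without bleeds known only from the parent record. A split into file and parent sources would not work, because sections 8.10.2.1 and 10.2 turn parent reports into file entries.
4. Report MBE and Non-MBE separately as well as combined.
5. In section 8.9, name the possible under-ascertainment of minor bleeds and its downward direction. This helps even for patients already followed.

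The cost is one line on an existing form, one eCRF field and some protocol wording. The Non-MBE incidence may look less favourable, and parent-recorded bleeds are harder to verify; the identification flag lets readers see how much they contribute.
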